3.3 Study Randomization, Stratification, or Description of Non-Random Assignment Procedures

3.3.1 Refine and Finalize HMP Stigma.

During Year 1, we will work with our technology partner, One Cow Standing (OCS), to build the HMP Stigma app. Once refinements are finalized, members of the research team, technology partner, and YAB will conduct internal usability testing of the app to ensure full functionality of HMP Stigma and the backend data-capture. All features of HMP Stigma will be tested during this time including ordering HIV test kits and HemaSpot protocols. OCS will fix any technical problems and finalize the platform for the RCT. The three domains to be modified in Year 1 are:

Technical Refinements: Technical refinements to HMP will focus on (1) the deployment of the peer-referral mechanism for participants assigned to the peer-referral HMP arm, and (2) system for ordering and tracking HemaSpot/HIV in-home test kits across three arms. We will also enhance our paradata tracking system, as we observed that many participants in the original HMP engaged with content (e.g., reading posts, viewing multimedia, scrolling through, liking content) even if they had not posted (these users are often termed "lurkers"). In HMP Stigma, we will extend our paradata metrics to collect detailed data on exposure and engagement with app content, whether as a contributor or lurker. This approach will allow us to fully track the underlying network structure of app engagement and its influence on the intervention's outcomes.

Modifications to Intervention Content: Modifications to intervention content will be informed by our prior results of HMP and the Stigma framework. We will bolster HMP's social support components to create a virtual space that elicits sharing and discussion from participants about their stigma-related experiences. The YAB will be significantly engaged in refining the final intervention content. YAB members will review a selection of the pre-populated Forum topics and the Knowledge Center's written content in terms of readability and relevance. In addition, we will elicit YAB member contributions of new content in terms of articles, forum posts, and discussion topics to reflect recent advances in HIV (e.g., PrEP, U=U), to be inclusive of our populations'

diverse identities around race/ethnicity, HIV status, and gender, and to make HMP feel "lived-in" before enrolling study participants.

Modifications to Promote User Engagement. In HMP Original, those who remained more engaged in the intervention had greater improvements in study outcomes. HMP Stigma will use multiple strategies to ensure participants are engaged with the intervention. First, we will employ and expand the most highly rated and frequently utilized features of the original HMP intervention (the Forum, Ask an Expert (provider Q&A), Knowledge Center and Quizzes). Second, we will convert the original HMP points-based reward system (which was not highly rated by participants) to a system whereby participants earn badges for completing activities and milestones within the app. We have used a similar badge system within a medication adherence app for YMSM which was rated with high acceptability by participants. We will further incentivize this system by releasing new badges throughout the course of the study.

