Peer-referred HMP Network Arm: Participants randomized to Intervention Arm 2 (peer-referred network) will be enrolled into a parallel (but separate) version of HMP Stigma. The only difference between Arm 1 and Arm 2 is that participants in Arm 2 will have a referral feature in their profile that allows them to earn \$20 in e-gift cards if they successfully refer and enroll 2 peers of their choosing (\$10 per peer) in the first 45 days of their study participation. The referral feature will create a customized link for each participant that can be emailed or text messaged to invite peers into the study. 189 Simple instructions will be provided at enrollment and in the app describing how to refer them. Participants may send referral links until two of their peers have screened eligible and enrolled in the study. Participants may send referrals from Day 1 – 45 of their time in the trial. If two of a participant's referred peers successfully enroll within that time window, at that point, the original participant will receive a notice from the study team that they have successfully reached their referral quota and the referral feature will deactivate. their referral incentives and HMP usernames of their referrals within their profile. While they will be able to see whether their peer has enrolled and what username the peer created, they will not receive any information about any of their peers' survey responses, including those who screened ineligible. Referred peers will see the HMP username of their referrer; they will not be eligible to refer their own peers.

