10.3.2.2 Qualitative Analyses

Using our latent class analysis of users' engagement profiles (e.g. high/low users, lurkers), we will select a subsample of up to 45 enrolled participants (approximately 5 from control and 20 per each intervention arm) across different sociodemographic and user engagement profiles to complete qualitative evaluation interviews (described above in section 5.4.5) Study staff, under the guidance of [name], will create a codebook of *a priori* and emergent themes including operational definitions of all codes and sample quotations to illustrate how to apply each code. Two study team members will use the codebook to independently code the data while a third team member will review these coded sections and resolve discrepancies. We will use Dedoose and Excel matrices to assist with theme identification, coding textual data, and describing relationships among codes (via code co-occurrence and memoing functions).²²¹ Analysis results will be used in conjunction with participants' survey responses, biological outcomes, and usage profiles to present a mixed methods intervention results analysis.

10.3.3 Specific Aim 3:

Specific Aim 3 is to examine whether changes in intersectional stigma and YBLMT's improvements across the HIV care continuum differ based on the network structure underlying user engagement in the two versions of HMP Stigma. To understand the role of social network dynamics between the two intervention conditions, we will compute social network parameters (e.g., size, density, centrality) for each version using the statnet and igraph packages in R.²²² Paradata indicators of active engagement (e.g., forum replies/likes) and passive engagement

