(e.g., reading forum posts) will be used to model threaded engagement networks between users. We will use these structures to describe types of users (e.g., discussion starters, contributors, lurkers), their location within the network (e.g., centrality), the frequency of exchanges between users (e.g., reciprocity), and presence of subgroups (e.g., cliques). Core social network metrics will be computed at the participant-level (e.g., centrality; popularity), as well as by stigma-related topic (e.g., trending, liked). We will use these network parameters to model (1) user engagement in HMP and (2) changes in HIV care continuum outcomes. We will use the general framework of generalized linear mixed models^{101–103} (GLMM) to model these longitudinal outcome trajectories. 110-112 Given that some of our outcomes are binary, some count and some continuous traits they will be treated differently (identity for continuous outcome, logit for binary outcome and natural log for count outcomes). We will use the estimated network parameters as covariates in our models, measuring how network characteristics are associated in differences in outcomes across the two treatment groups. In addition, GLMM also allows us to link YBLMT's individual trajectories with social network changes by adding them as time-varying covariates. For example, one analysis will examine how changes in networks' characteristics effect changes in YBLMT's VS, after adjusting for changes in stigma. These follow a network autocorrelation metric, whereby a term is added to the general model to captures a (weighted) average of peers' outcomes. Exploratory analyses will determine if random effects should be included. Maximum likelihood estimation will be used for fixed effects. To ensure robustness, we will also apply an exchangeable working correlation structure to its corresponding generalized estimating equation model. 104

Note: Any deviations from the analysis plans outlined above or in the sections that follow will be documented and justified in the Statistical Analysis Plan developed for this protocol.

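### Aim 3 adds a peer-outcome term to in-app networks but specifies no use of the recorded nominator-peer ties, so prior similarity in Arm 2 can be read as online influence

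*Combined protocol and SAP*

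**What the plan says.** Section 3.3.1 (Technical Refinements) describes the extended paradata and states: "This approach will allow us to fully track the underlying network structure of app engagement and its influence on the intervention's outcomes". Section 10.3.3 sets out how the networks are made. "Paradata indicators of active engagement (e.g., forum replies/likes) and passive engagement" ("e.g., reading forum posts) will be used to model threaded engagement networks between users") are the only sources of ties it names. The resulting measures enter the models: "We will use the estimated network parameters as covariates in our models". The peer-influence component is a network autocorrelation term, for which "a term is added to the general model to captures a (weighted) average of peers' outcomes". The one worked example concerns viral suppression, "after adjusting for changes in stigma". Whether to include random effects is left to exploratory analysis with no level named, and the clustering unit of the GEE check is not given.

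The referral ties are described elsewhere. Section 3.3.2 says: "The only difference between Arm 1 and Arm 2 is that participants in Arm 2 will have a referral feature in their profile". Each nominator has an individual link, may bring in two peers, and nominator and peer see each other's usernames. Section 5.3 leaves referred peers unrandomized so that they stay clustered with their nominator. Section 5.1 puts referred peers at 300, two thirds of Arm 2. Nothing in Section 10 names the referral tie as a network edge, a covariate or a cluster.

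**The concern.** Aim 3 asks whether stigma and care outcomes differ between the two app versions because of their network structure. In Arm 2 the forum network lies on top of existing acquaintance; in Arm 1 it does not, by design. Friends tend to resemble one another before either opens the app, and mutual visibility of usernames makes it plausible that they read and answer each other. A term that averages the outcomes of forum contacts cannot tell that resemblance from influence exerted online.

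At stake is a secondary conclusion: that the peer-referred network transmits behaviour more strongly than the researcher-created one. An error here would favour the hypothesis in Section 1.2 that peer referral does better. The reference list includes a paper on the confounding of homophily with contagion in observational network studies, but the analysis text has no step that deals with it.

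**Working it through.** **Counts (Section 5.1).** 150 nominators × 2 = 300 referred peers. 300 / (150 + 300) = two thirds of Arm 2, as stated, and 750 + 300 = 1,050, the planned total. So there are up to 300 nominator-peer ties among 450 × 449 / 2 = 101,025 possible Arm 2 pairs (0.3%), and none by design in Arm 1.

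**Quantities the documents do not give (assumed).** The outcome correlation within a referral group (ICC), and how much of a user's in-app contact is with referral partners.

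**Check 1: cross-sectional, no true influence.** 150 groups of three. The peer average puts weight w on the two group mates and 1 − w on eight unrelated users. With outcome variance 1, the mates' mean has covariance ICC with one's own outcome and variance (1 + ICC)/2. The mean of the eight others has covariance 0 and variance 1/8. The expected false coefficient is therefore

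w·ICC / [w²(1 + ICC)/2 + (1 − w)²/8].

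| ICC | w | Formula | Simulated | False positives |
|---|---|---|---|---|
| 0.05 | 25% | 0.0125/(0.0328 + 0.0703) = 0.12 | 0.11 | 20% |
| 0.10 | 25% | 0.0250/(0.0344 + 0.0703) = 0.24 | 0.23 | 38% |
| 0.20 | 25% | 0.0500/(0.0375 + 0.0703) = 0.46 | 0.48 | 89% |
| 0.30 | 10% | 0.0300/(0.0065 + 0.1013) = 0.28 | 0.28 | 47% |
| 0.30 | 0.5% | 0.0015/(0.0000 + 0.1238) = 0.01 | 0.01 | 8% |

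(400 runs per cell, nominal 5%.) With no referral similarity, as in Arm 1, the coefficient is 0.00 with 7% false positives. With the mates' mean entered as its own term, the coefficient on the other contacts lies between −0.013 and 0.012 in every cell, with 4–8% false positives.

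**Check 2: lagged model, closer to a longitudinal analysis.** Outcome = group effect + person effect + noise, with no influence between people and a within-person correlation of 0.5. The later outcome is regressed on one's own earlier outcome and on the mean earlier outcome of forum contacts, with standard errors clustered on the referral group. Assumed: 80% of referral pairs are also tied on the forum, with about five other ties each.

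| Within-group correlation | 0.1 | 0.2 | 0.3 |
|---|---|---|---|
| Continuous, all users: false coefficient | 0.05 | 0.10 | 0.15 |
| Continuous, all users: false positives | 10% | 19% | 35% |
| Binary viral suppression, HIV-positive only: false positives | 7% | 9% | 14% |
| The same, referral ties given triple weight | 8% | 16% | 26% |

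The HIV-positive rows use about 300 users: 150 nominators plus half of the 300 peers, following the assumption in Section 3.2. Splitting the term in the continuous case returns the forum coefficient to about 0, with 4–7% false positives.

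**Check 3: would a referral-group random intercept do instead?** In the continuous lagged model with triple weight on referral ties, it left false positives of about 11%/47%/79% at correlations 0.1/0.2/0.3.

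**Check 4: change on change.** With a constant group effect, differencing cancels the similarity: the coefficient was about −0.01 at every correlation tried.

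**The case against.** The strongest reply is that the bias is conditional and its inputs are invented. That stands. If referral partners hardly meet in the app, the effect vanishes, and 300 ties is the planned maximum: nominators have 45 days and a quota of two.

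HIV status also limits the problem. All nominators are HIV-positive, and about half of their peers are assumed not to be. For routine testing, a nominator has no such outcome, so nominator-peer ties cannot create the similarity. For viral suppression only part of the ties count, which is why that row is so much lower. The larger figures apply only to outcomes that everyone shares, such as stigma scores. The worked example in Section 10.3.3 speaks of changes predicting changes, and in a literal form of that model the bias may not arise. The plan does not fix one form, and a GLMM on levels would not cancel it.

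Some stronger readings are tempting, but the documents do not support them:

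- A reader might infer that the sentence in Section 3.3.1 is false. It claims only to track the network of app engagement, so it is not wrong in itself; the gap is in Section 10.3.3.
- A reader might infer that the Arm 2 influence term is certain to be inflated. Neither quantity that decides this is given.
- A reader might infer that the trial plans a formal test of influence by arm. None is stated, and Section 5.4.1 frames this part as describing network composition.
- A reader might infer that referral ties will definitely be ignored. The table of potential covariates cited in Section 5.4.4 is not in the text available, and the random-effect and GEE units are open. What can be said is that no use is specified.
- A reader might treat cliques and reciprocity produced by referral as contamination. Bringing in friends is the Arm 2 intervention, so these features are part of what Aim 3 sets out to describe.

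**Conclusion.** The point holds in conditional form. Section 10.3.3 specifies no use of a recorded tie that exists by design in one arm only, while adding a term that would absorb similarity along that tie. If referral partners have similar outcomes and interact in the app, prior similarity can be read as online peer influence in Arm 2, and Arm 1 has no such route.

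The size is unknown. Under the assumptions shown, inflation runs from negligible to several times the nominal 5% for outcomes shared by all users, and is modest for viral suppression. The figures are illustrations, not estimates for this trial. Aim 3 is secondary, so this should be corrected but does not threaten the trial's main comparison.

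**What to change.** In Section 10.3.3:

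1. Carry the referral link as a known tie type, separate from forum ties.
2. Split the peer-outcome term into (a) the average over referral partners and (b) the average over other forum contacts. Report both.
3. Compare Arm 1 with Arm 2 on online peer influence using (b). Describe (a) as a mixture of prior similarity and real nominator-peer exchange, so that the exchange is reported and not discarded.
4. Report Arm 2 centrality, reciprocity and clique measures with and without nominator-peer ties, as description and not as a correction.

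The cost is some SAP wording, a little programming on data already held, and slightly less precision for the forum term because some ties move out of it. The change removes only the part specific to Arm 2. Similarity among users who seek each other out on the forum remains in both arms and should be stated as a limitation.

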3.3.2 Intervention and control arms

Participants in all arms will have access to a Care Navigator through the intervention or control app. The Care Navigator will utilize existing online databases of resources (e.g. AIDSVu.org Locators, CDC's GetTested.cdc.gov locators, POZ.com's Service directory) to connect participants to trusted HIV testing and care services in their communities as needed. The Care Navigator will also monitor the Forums to identify additional HIV knowledge needs and manage the Ask an Expert provider Q&A to triage medical questions to one of two board-certified HIV care providers. During all study years the Care Navigator will work closely with the YAB to elicit service-related needs and concerns among YBLMT that can be integrated into HMP Stigma.

Control Arm: The HMP Stigma Information-Only Control Arm will feature a streamlined version of the app that provides curated information and other content for YBLMT. This content will follow the design of HMP Original where control arm participants had access to HIV-related Knowledge Center articles of the main intervention without access to the engagement features such as the interactive forums or doctor Q&A. HIV-negative and sero-unknown participants will also be able to request HIV home test kits. Our choice of control arm balances equipoise with research study design; in HMP Original, control arm participants also experienced a statistically significant intervention benefit.⁴⁷ We have taken this effect into account in our sample size calculations.

HMP Stigma: We have used the Stigma Framework¹²⁸ alongside our findings from HMP Original to guide the design of our proposed intervention features and content (Table 1) and study measures (Table 2). Eligible, enrolled participants who are randomized to intervention Arms 1 (researcher-created network) and 2 (peer-referred networks) will have access to all the features of HMP Stigma. These features include forums where users can start or participate in threads, a knowledge center filled with short articles on a range of topics that can be added and commented on, a provider platform where health questions can be submitted to be answered by a health care provider, a user profile where users can personalize and update their information, and finally, an ordering platform where users can order and track testing kits.

Table 1: HMP Stigma Core Intervention Components and Scientific Rationale						
Intervention Feature & Description	Scientific rationale	Paradata metrics ^a				

HMP Forums: Discussion boards where users can start new discussion threads or respond to or "like" content posted by other participants.	Pre-populated thread topics will correspond to stigma framework constructs.	# of: posts created, posts read/liked; total time spent; content of posts
Knowledge Center: Brief articles on health and wellness tailored for YBLMT, including featured sections on HIV/STI prevention and care.	Content will correspond with original HMP intervention, and aligns with the Integrated Behavior Model.	# of: articles read, quizzes completed; total time spent
Provider Platform: HIV/STI/sex questions answered by a prevention and HIV care doctor within 72 hours.	Provide evidence-based answers to users' health questions, including linkage to care.	# of: posts created, posts read; total time spent; content of questions
User Profile: Profile page showing participant's username, favorites, and badge progress.	Personalization and gamification features may incentivize continued user engagement.	# of: times visited, badges earned
Test ordering: Ability to order HIV self-test kit.	Provide an opportunity to get tested if users experience barriers to get tested locally.	# tests ordered

^a Each unique user action on HMP will be captured with date and timestamps.

Peer-referred HMP Network Arm: Participants randomized to Intervention Arm 2 (peer-referred network) will be enrolled into a parallel (but separate) version of HMP Stigma. The only difference between Arm 1 and Arm 2 is that participants in Arm 2 will have a referral feature in their profile that allows them to earn \$20 in e-gift cards if they successfully refer and enroll 2 peers of their choosing (\$10 per peer) in the first 45 days of their study participation. The referral feature will create a customized link for each participant that can be emailed or text messaged to invite peers into the study. 189 Simple instructions will be provided at enrollment and in the app describing how to refer them. Participants may send referral links until two of their peers have screened eligible and enrolled in the study. Participants may send referrals from Day 1 – 45 of their time in the trial. If two of a participant's referred peers successfully enroll within that time window, at that point, the original participant will receive a notice from the study team that they have successfully reached their referral quota and the referral feature will deactivate. their referral incentives and HMP usernames of their referrals within their profile. While they will be able to see whether their peer has enrolled and what username the peer created, they will not receive any information about any of their peers' survey responses, including those who screened ineligible. Referred peers will see the HMP username of their referrer; they will not be eligible to refer their own peers.

4.0 SELECTION AND ENROLLMENT OF STUDY PARTICIPANTS

4.1 Inclusion Criteria (All study arms)

- Aged 15-29 years (inclusive) at time of screening
- Identify as Black/African American and/or Latino/Hispanic
- Current U.S. resident (verified by zip code)
- Speak and read English
- Report anal intercourse in the past 6 months
- Assigned male sex at birth (no restrictions on current gender identity)
- Has a smartphone
- If HIV-positive, does not report a hemophilia diagnosis or current use of anti-coagulation medication

Additional Inclusion Criteria (Referred Peers from Peer-Referral Arm)

- Invited by current participant in Intervention Arm 2 (approximately 300 participants)
- Any race/ethnicity

